9.2 Data Collection and Management

Data will be managed and stored by the University of Utah Data Coordinating Center (DCC), which has an established working relationship with PECARN (the planned research network for the subsequent multicenter pragmatic trial). We will work with the DCC to create the electronic case report form (CRF) for this study. The CRF will be password-protected with the safeguards noted below to maintain confidentiality for all data entered into the CRF. The CRF will be password-protected and entered via CHOP-issued computers. There will be a separate master list linking subject PHI and study data and will be stored separately from the study data and will only be accessible to the CHOP study team. Locally secured, identifiable information and partially identifiable information will be stored locally at CHOP for this pilot study.

The Data Coordinating Center has a state-of-the-art computer infrastructure with a dedicated server room with a fire suppression system, air conditioning, cooling system and separate air filtering. The server facility is locked separately from the remainder of the Data Coordinating Center and access to the building is monitored by security personnel year round. The Data Coordinating Center coordinates its network infrastructure and security with the Health Sciences Campus (HSC) information systems at the University of Utah. This provides the Data Coordinating Center with effective firewall hardware, automatic network intrusion detection, and the expertise of dedicated security experts working at the University.

Network equipment includes four high-speed switches. User authentication is centralized with two Windows 2008 domain servers. Communication over public networks is encrypted

with virtual point-to-point sessions using SSL or VPN technologies, both of which provide at least 128 bit encryption. REDCap, OpenClinica (Web-based clinical studies data management system), eRoomTM (Web-based collaborative workspace) and other web applications use the SSL protocol to transmit data securely over the Internet. Direct access to Data Coordinating Center machines is only available while physically located inside the Data Coordinating Center offices, or via a VPN client. All network traffic is monitored for intrusion attempts, security scans are regularly run against our servers, and IT staff are notified of intrusion alerts.

Production servers running mission critical applications are clustered and configured for failover events. Servers are backed up with encryption through a dedicated backup server that connects across an internal 10 gigabit network to a tape drive. Storage area networking (SAN) applications, clusters, and switch-to-switch links are also on a 10 gigabit network. Incremental backups occur hourly during the week. Incremental backups also are performed nightly with full system backups occurring every week. Tapes are stored in a fireproof safe inside the data center facility, and full backups are taken to an off-site commercial storage facility. Security is maintained with Windows 2008 user/group domain-level security.

Users at both CHOP and University of Utah will be required to change their passwords every 90 days, and workstations at University of Utah will time out after 5 minutes of inactivity. All files are protected at group and user levels; database security is handled in a similar manner with group level access to databases, tables, and views in Microsoft SQL Server. All portable computers at University of Utah are whole-disk encrypted.

9.3 Confidentiality

All data and records generated during this study will be kept confidential in accordance with Institutional policies and HIPAA on subject privacy and the Investigator and other site personnel will not use such data and records for any purpose other than conducting the study.

The PI and other research personnel have all completed training and received certification in Human Subjects Research Protection and HIPAA. All project staff hired will also successfully complete this training prior to engaging in any research or treatment with study participants and renew this training as required by their institution.

The investigators and staff of the Data Coordinating Center are fully committed to the security and confidentiality of all data collected for the PRoMPT Bolus-Feasibility study. All Data Coordinating Center personnel at the University of Utah have signed confidentiality agreements concerning all data encountered in the center. Violation of these agreements may result in termination from employment at the University of Utah. In addition, all personnel involved with data coordinating center data systems have received Human Subjects Protection and HIPAA education.

The staff, reviewers and investigators involved with this study will be required to sign agreements from the Data Coordinating Center that relate to maintenance of passwords, information system security, and data confidentiality.

No identifiable data will be used for future study without first obtaining IRB approval. The investigator will obtain a data use agreement between the provider (the PI) of the data and any recipient researchers (including others at CHOP) before sharing a limited dataset (PHI limited to dates and zip codes).

9.4 Regulatory and Ethical Considerations

9.4.1 Data and Safety Monitoring Plan

The principal investigator will be responsible for overseeing data collection and the safety of all study procedures. In addition, a Data Safety Monitoring Board (DSMB) will be convened made up of representatives who are independent of the study investigators.

Before initiation of the clinical study, the sponsor-investigator will arrange a pretrial monitoring visit with the IND & IDE Support Program and the Office of Research Compliance (ORC) to confirm clinical trial readiness. After enrolling and starting administration of the investigational agent to the first subject, the sponsor-investigators will contact ORC to arrange a monitoring visit. Thereafter, ORC will monitor the study at least once during the course of the pilot. Monitoring activities will be guided by ICH E6 section 5.18. Monitoring of subject data will be initiated at 100% verification of the data recorded. This may be amended, and a tapered approach to monitoring may be employed, if conduct and documentation of the study reaches a level of reliability that would permit valid conclusions based upon a sampling of data

9.4.2 Data Safety Monitoring Board (DSMB)

The PRoMPT Bolus – Feasibility study will have a Data Safety Monitoring Board (DSMB) composed of five members from the CHOP/University of Pennsylvania community who have no other involvement in any aspect of the proposed study. Members of the DSMB will be invited by the study investigators in consultation with the DCC. At least one member will be knowledgeable in medical ethics and at least one member will be a patient advocate. The DSMB will have a charter, will approve the protocol prior to implementation, and will meet prior to initiation of subject enrollment, after hospital discharge of the first 36 subjects, and again at the conclusion of the study along with meetings scheduled *ad hoc* as necessary.

The purpose of the DSMB will be to advise the study investigators regarding the continuing safety of study subjects and the continuing validity and scientific merit of the study. The DSMB is responsible for monitoring accrual of study subjects, adherence to the study protocol, assessments of data quality, review of serious adverse events and other subject safety issues, and review of formal statistical analyses. The DCC will send reports relating to these topics to DSMB members ten days prior to each DSMB meeting and will notify the DSMB if the mortality difference exceeds the predetermined stopping rule noted in Section 6.5.

The DCC will remotely staff DSMB meetings and produce minutes of open sessions. Minutes of closed or executive sessions of the DSMB will be produced and retained by the DSMB Chairperson. These closed minutes will not be available outside the DSMB prior to the end of the study.

The DSMB Chairperson will prepare a summary of each DSMB meeting that conveys the public conclusions of the DSMB, with respect to protocol alterations and recommendations concerning continuation of the study. The summary will be provided to the DCC and the DCC will send this summary to all participating investigators for submission to their respective Institutional Review Boards.

The DSMB will meet prior to the start of subject enrollment and then after enrollment of all subjects for this feasibility study. The DSMB, however, will have the discretion to alter meeting timing and frequency, as well as meet ad hoc as necessary throughout the course of the study.

9.4.3 Risk Assessment

Because both NS and LR have both been previously proven as efficacious for fluid resuscitation of pediatric septic shock, both NS and LR are currently used in common clinical practice for this indication, and because patients will only be considered eligible if the clinical care team (usually the attending physician) deems it safe for the patient to receive both NS and LR, the risks presented by this study will be limited. However, because there is a prospect of a relative benefit in efficacy and/or safety for one fluid over the other, subjects may be randomized to an arm with relatively inferior efficacy or relatively worse safety.

Several safeguards have been put in place to minimize risk of randomized (rather than clinician-prescribed) fluid administration, including:

- a) Because of the FDA noted caution in using lactate-containing fluids, such as LR, in patients <6 months of age, only patients >6 months-old will be eligible for this study.
- b) Any patients for whom clinician judgement deems it unsafe to administer NS or LR will be excluded from enrollment, with specified exclusions noted (but not limited to) clinical suspicion for impending brain herniation, known hyperkalemia, known hypercalcemia, and known fulminant hepatic failure.
- c) Exclusion of patients with known pregnancy, known prisoner status, or known allergy to NS or LR.

In addition, post-marketing risks reported with infusion of either NS, LR, or both fluids are listed in Table 4. All of these risks that have been reported with (but not necessarily causally linked to) use of either NS, LR, or both and are all consistent with the risks subjects would experience if they received these fluids as part of clinical care. Therefore, participation in this study is unlikely to expose patients to risks beyond that incurred as part of routine clinical care. However, since it is likely that more patients will receive LR than otherwise would as part of routine clinical care, there may be a slight increase in risk for the study population as a whole than would otherwise be the case as part of routine clinical care.

Table 4: Reported risks associated with infusion of NS and/or LR

Risk	Reported with NS	Reported with LR
Anaphylaxis/anaphylactoid reaction	X	X

Angioedema/Laryngeal edema	X	X
Chest pain/chest discomfort	X	X
Bronchospasm		X
Dyspnea/Respiratory distress	X	X
Cough	X	X
Urticaria or other rash	X	X
Pruritis	X	X
Nausea	X	X
Pyrexia	X	X
Infusion site reaction (erythema, pruritis, numbness, pain, edema, extravasation)	X	X
Bradycardia		X
Tachycardia		X
Hypotension		X
Anxiety	X	X
Headache	X	X
Dysgeusia (metallic taste in mouth)		X
Paresthesias		X
Sneezing		X
Hyperkalemia	X ^a	X
Hypervolemia	X	X
Pulmonary edema	X	X
Acid-base disturbance	X ^a	X
Hyponatremia		X
Hyperlactatemia		X
Hypernatremia	X	

Hyperchloremia	X	
Hypercalcemia		X
Acute kidney injury	X ^a	X
Infection	X ^a	X
Coagulopathy	X	X
Venothromboembolism	X	X ^b
Cerebral edema	X	X ^b

^aRisk reported in patients receiving both NS and LR but may be more common with NS

^bRisk reported in patients receiving both NS and LR but may be more common with LR

The other major risk to subjects enrolled in this study is breach of patient confidentiality, which is itself limited by the safeguards noted in Section 8.3.

9.4.4 Potential Benefits of Trial Participation

Because fluid resuscitation with either NS or LR may offer relative superior efficacy and/or safety, there is a prospect of direct benefit to subjects from trial participation.

Additionally, indirect benefits to society are clear because this pilot study will help to inform a larger pragmatic comparative effectiveness study to meet the needs of clinicians making treatment decisions about fluid resuscitation for pediatric patients with suspected septic shock. By informing the most beneficial and safe crystalloid fluid for clinicians to select, society (and future patients) may benefit from a reduction in sepsis-associated morbidity and mortality.

9.4.5 Risk-Benefit Assessment

Because NS and LR are both known to be efficacious for resuscitation of pediatric septic shock and both fluids are currently used in clinical practice, there is a minimal expected impact on the overall risk-benefit balance to patient to participation in this trial beyond that which would be incurred as part of ordinary routine clinical practice. Nonetheless, because subjects enrolled in this study will receive type of fluid determined by randomization rather than clinician-prescribed (as in usual practice) and there is a potential for a relative benefit in efficacy and/or safety for one fluid over the other, the risks incurred by enrollment in this study may be slightly higher than in clinical practice. However, this small potential for risk for subjects randomized to a relatively inferior fluid is balanced by the prospect of direct benefit for subjects randomized to a relatively superior fluid with all subjects having an equal chance of randomization to either arm. The primary benefit of this trial for patients is that each patient has a random chance to be exposed to a potentially more effective fluid resuscitation strategy. Given the lack of definitive data indicating which fluid is more effective and, thus equipoise, it cannot be known before the study which fluid arm may or

may not provide the most benefit. Risks due to breach of confidentiality are another risk, but this will be mitigated by the steps outlined in Section 8.3.

Given the potential of direct patient benefit with only minimal risk greater than routine clinical care, the study is justified to proceed based on the balance between risks and benefits.

9.5 Recruitment Strategy

Subjects will be recruited as part of routine clinical practice within the CHOP pediatric ED. Prospective subjects will be identified by the clinical care team when they meet eligibility criteria. We anticipate that activation of the CHOP ED Sepsis Pathway order set will be a primary trigger to consider eligibility for inclusion of a patient in this study. However, patients do not necessarily have to be treated on the CHOP ED sepsis pathway to be considered for eligibility of enrollment into this study. A member of the study team—including ED attendings and fellows included and trained as study co-investigators—will ensure subjects meet all eligibility criteria prior to study enrollment. After eligibility is confirmed and, in the rare cases where sufficient time is available for prospective informed consent, a member of the study team—including ED attendings and fellows included and trained as study co-investigators—will seek informed consent. For most cases, however, we anticipate that conditions will not permit sufficient time for prospective informed consent and we will proceed with enrollment under Exception From Informed Consent (EFIC, see Section 9.6.3) for which a member of the clinical care team, under the supervision of the attending physician of record or his/her designee, will be responsible for obtaining an “opt-out” from the LAR when possible (see Section 9.6.3 for further details of “opt-out” plan). Study fliers (approved under CHOP IRB study 17-013950) will be posted in the CHOP ED to further inform potential subjects and LARs of this study.

Based on internal data from CHOP and published estimates,⁵³ we anticipate 189-290 eligible patients per 100,000 ED visits. With approximately 20,000 visits over 4 months to the CHOP ED, we anticipate sufficient subjects to achieve the study goals with enrollment over 4 months.

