Setting/Participants: Eligible patients >6 months and <18 years with clinician concern for septic shock who require at least 20 ml/kg of fluid resuscitation will be enrolled in the Emergency Department of the Children’s Hospital of Philadelphia. Patients will be enrolled prior to receipt of >40 mL/kg IV/IO crystalloid fluid. Due to the life-threatening nature of septic shock and the narrow therapeutic window for fluid resuscitation, potential subjects will be enrolled through the federal “exception from informed consent” (EFIC) process, with prospective informed consent obtained as possible in rare circumstances.

Study Interventions and Measures: Seventy subjects will be randomized to receive either open-label NS or LR for all remaining fluid administration (bolus and maintenance) until 11:59pm on the calendar day following randomization such that all patients receive at least 24 hours of study fluid. The primary feasibility outcome for this pilot study will be the proportion of total crystalloids administered as the correct study fluid within each randomized arm (Aim 1). Secondary outcomes will include mean proportion of total crystalloids administered as non-study fluid in each arm (Aim 1), percent enrollment/randomization/treatment of eligible patients (Aim 2), and successful EFIC approval with <10% subject withdrawal. Specified safety outcomes will be monitored as they occur in the course of routine clinical practice but this pilot study will not be powered to assess safety given that both fluids are FDA-approved and have well-described efficacy and safety profiles.

PROTOCOL SYNOPSIS

Study Title	Feasibility Study for the Randomized Pragmatic Pediatric Trial of Balanced versus Normal Saline Fluid in Sepsis (PRoMPT BOLUS – Feasibility)
Funder	The Children's Hospital of Philadelphia
Clinical Phase	Pilot/feasibility study

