3.3.2 Total Number of Study Sites/Total Number of Subjects Projected

The study will be conducted at one investigative site in the United States (the Children's Hospital of Philadelphia). The University of Utah will act as the Data Coordinating Center (DCC) for this study, but they will not be engaged in human subjects research. Their role is limited to the receipt of a limited dataset from the CHOP investigators.

Recruitment will stop when 70 subjects are enrolled and randomized. It is expected that approximately 80 eligible subjects will be enrolled to produce 70 evaluable subjects.

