sepsis/septic within 24 hours of ED presentation were missed.⁴⁸ However, because the positive predictive value of this combined approach was 25.4%, we have required the additional inclusion criterion of administration of at least 20 mL/kg IV/IO fluid resuscitation with additional fluid deemed likely to be necessary to treat poor perfusion, defined as either hypotension or abnormal (either “flash” or >3 second) capillary refill (as determined by clinician’s judgment).

- 3) Administration of at least 20 mL/kg IV/IO fluid resuscitation
- 4) Receipt of ≤ 40 mL/kg IV/IO crystalloid fluid prior to randomization
- 5) Additional fluid deemed likely to be necessary to treat poor perfusion, defined as either hypotension or abnormal (either “flash” or >2 second) capillary refill (as determined by clinician’s judgment)¹⁰

NOTE: Due to the pragmatic nature of this study that is designed to reflect usual clinical practice, we will not define specific thresholds for either hypotension or abnormal capillary refill but rather defer to the treating clinician’s discretion to determine hypotension and abnormal capillary refill.

- 6) Parental/guardian permission (informed consent) if time permits; otherwise, EFIC criteria met

NOTE: For patients who may be transferred to the CHOP ED from an outside facility, many will have started fluid resuscitation prior to arrival in the CHOP ED. If volume of crystalloid fluid administration cannot be easily determined such that receipt of ≤ 40 mL/kg IV/IO crystalloid volume cannot be easily verified, these patients will be operationalized as not meeting the ≤ 40 mL/kg inclusion criterion.

NOTE: Patients who are randomized to a study arm at ≤ 40 mL/kg crystalloid fluid resuscitation *but for whom study fluid is not initiated until after >40 mL/kg* will still be included and should commence with administration of study fluid for the duration of the remaining intervention phase.

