relative difference in efficacy or safety for use of NS versus LR on the developing fetus during any trimester,⁴⁹ there is no specific need to exclude pregnant women from the interventions to be tested in this study beyond the requirements for enrollment under “exception from informed consent”. In addition, since 2012, none of the 1,420 patients treated for sepsis in the CHOP ED has had a positive pregnancy test. Therefore, because waiting for biochemical testing for pregnancy (e.g., urine β -HCG) would either cause most post-pubertal female patients become ineligible for enrollment (due to receipt of >40 mL/kg of fluid) or delay fluid resuscitation (putting potential subjects at risk of harm) *and* given the extremely low risk for diagnosing pregnancy in this patient population *and* given the safe use of both NS and LR in pregnancy, there will not be a requirement to delay study enrollment while awaiting results of a pregnancy test. Any subject enrolled in the study who is subsequently determined to be pregnant as part of routine clinical care, which at CHOP includes testing for pregnancy in all female patients of child-bearing age, will be immediately withdrawn from this study.

- 3) Known prisoner as determined by routine social history disclosed by patient and/or LAR (or other accompanying acquaintance)
- 4) Known allergy to either normal saline or lactated Ringer's as determined by routine allergy history disclosed by patient and/or LAR (or other accompanying acquaintance) or as indicated in the medical record
- 5) Indication of prior declined consent to participate based on presence of a “PRoMPT BOLUS Opt-Out” bracelet with appropriate messaging embossed into the bracelet (see IRB study 17-013950) or the presence of the patient's name on an opt-out list that will be kept up-to-date and checked prior to randomization.

Concurrent participation in another interventional trial will not be considered an exclusion criteria because such co-enrollment is not expected to impact the feasibility aims and outcomes for this study.

Subjects that do not meet all of the enrollment criteria may not be enrolled. Any violations of these criteria must be reported in accordance with IRB Policies and Procedures.

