6.3.2 Feasibility Analysis

The primary analysis will be based on an intention-to-treat approach and will include all subjects randomized whether or not study fluid was administered.

The primary endpoint will be defined as meeting feasibility criteria if either of the following criteria are met:

- 3) There is an absolute difference in the mean use of NS between arms of at least 65% with a lower 95% CI border of >60%. For example, feasibility criteria would be met if 90% of crystalloid fluid in the NS arm was NS compared to only 25% in the LR arm. The proportion of NS use in each arm will be compared using the chi-squared test with a 95% bootstrap confidence interval with bias correction (assuming skewed distribution of data) around the difference in the proportion of NS use in each arm.
- 4) At least 85% of subjects in the NS arm receive $\geq 90\%$ of study fluid as NS during the study window *and* at least 80% of subjects in the LR arm receive $\geq 75\%$ of study fluid as LR.

The secondary endpoints will be defined as meeting feasibility criteria if:

- The mean proportion of total crystalloids administered as non-study fluid (i.e., cross-over) is $\leq 25\%$ in each arm (for example, $\leq 25\%$ of total crystalloid is administered as NS for patients randomized to the LR arm).
- The proportion of eligible patients treated in the pediatric ED who are enrolled, randomized, and treated with study fluid is $>65\%$.
- EFIC is approved by the IRB at CHOP
- The proportion of eligible patients who meet criteria for EFIC who are not enrolled or who are enrolled but withdraw prior to completion of the follow-up phase is $\leq 10\%$.

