6.4 Sample Size and Power

In a previous PECARN study called the FLUID trial (data not yet published), nearly 1400 pediatric patients presenting to the ED with diabetic ketoacidosis (DKA) were randomized to different fluid volumes and different fluid types (normal saline vs. half-normal saline).

We used FLUID data on adherence to fluid type assignment to simulate adherence in the proposed study, assuming that the LR arm will behave like the half-NS arm (i.e., the study intervention arm) and the NS arm will behave like the NS arm (i.e., the control arm) in the FLUID trial. In the FLUID trial, the mean percentage of correct fluid given was 96% in the NS arm and 91% in the half-NS arm. About 90% of subjects in the NS arm received at least 85% NS, while about 89% of those in the half-NS arm received at least 75% half-NS. Through simulation, by sampling from FLUID data, with 35 patients in each arm, the probability that at least 85% of subjects in the NS arm and 80% in the LR arm will receive the “adequate” amount of correct study fluids (i.e., $\geq 90\%$ of study fluid as NS in NS arm and $\geq 75\%$ of study fluid as LR in the LR arm) is approximately 80% (study power for criterion #2 of the Aim 1 feasibility analysis described in Section 6.3.2).

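### The four-month accrual forecast in section 9.5 is not supported by its own inputs, which give about 38 to 58 eligible patients against 70 to be randomized

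*Combined protocol and SAP*

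**What the plan says.** Section 9.5 (Recruitment Strategy) gives the forecast in two sentences. The inputs are: "we anticipate 189-290 eligible patients per 100,000 ED visits. With approximately 20,000 visits over 4 months to the CHOP ED". The conclusion is: "we anticipate sufficient subjects to achieve the study goals with enrollment over 4 months". No expected count is printed.

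The target is stated elsewhere. The Abstract says "Seventy subjects will be randomized to receive either open-label NS or LR". Section 3.3.2 says "Recruitment will stop when 70 subjects are enrolled and randomized", and adds that about 80 are expected to be enrolled to leave 70 evaluable. The Synopsis lists 80 subjects. The simulation in section 6.4 is run "with 35 patients in each arm", which is 70 in total. There is one site.

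The documents give no other eligibility rate and no other accrual window. One further volume figure appears in the pregnancy note of section 3.4.2: "since 2012, none of the 1,420 patients treated for sepsis in the CHOP ED has had a positive pregnancy test". It has no end date.

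**The concern.** The rate, the visit count and the conclusion stand in the same paragraph, and the first two do not lead to the third. The rate is already expressed per eligible patient, so no later step can raise the yield. Missed patients, pre-enrollment opt-outs and refusals can only lower it.

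This is the only accrual forecast in the documents, and the study exists to judge whether a larger trial can recruit. If the forecast is wrong, the time for which staff training, the opt-out list and the monitoring arrangements must be kept up is understated. If the rate is wrong, the reader has no sound figure for the number of eligible patients to expect.

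**Working it through.** **Inputs**

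- Eligible rate: 189 to 290 per 100,000 ED visits (section 9.5).
- Visits: about 20,000 in 4 months, or 5,000 a month (section 9.5).
- Target: 70 randomized (Abstract, sections 3.3.2 and 6.4). About 80 enrolled is the alternative (Synopsis, section 3.3.2).
- Capture, meaning the share of eligible patients who are enrolled: no forecast is given. I use 100% as the most favorable case, 90% as an illustration, and 65% because it is the Aim 2 pass mark in section 6.3.2. The 65% is also only an illustration.

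**Expected eligible patients in 4 months = visits × rate**

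- Lower rate: 20,000 × 189/100,000 = 37.8, and 37.8/70 = 54%.
- Upper rate: 20,000 × 290/100,000 = 58.0, and 58.0/70 = 83%.

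The shortfall against 70 is 12 to 32 patients, a factor of 70/58.0 = 1.2 to 70/37.8 = 1.9. Against 80 enrolled, the yield is 47% to 73%. The claim of sufficiency is therefore not reproduced at either end of the range.

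**Chance of at least 70 in 4 months (Poisson count with mean = visits × rate × capture)**

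| Rate per 100,000 | Capture | Mean | P(70 or more) |
|---|---|---|---|
| 290 | 100% | 58.0 | 6.9% |
| 290 | 90% | 52.2 | 1.1% |
| 290 | 65% | 37.7 | about 2 in a million |
| 189 | 100% | 37.8 | about 2 in a million |

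**Expected months to target = target / (5,000 × rate × capture)**

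Monthly eligible patients are 5,000 × 0.00189 = 9.45 to 5,000 × 0.00290 = 14.5.

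- To 70 at 100% capture: 70/14.5 = 4.8 to 70/9.45 = 7.4 months.
- To 70 at 65% capture: 4.83/0.65 = 7.4 to 7.41/0.65 = 11.4 months.
- To 80 at 100% capture: 80/14.5 = 5.5 to 80/9.45 = 8.5 months.

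**What four months would need, on average, for 70**

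- With 20,000 visits: 70/20,000 = 350 per 100,000 at 100% capture, or 350/0.65 = about 538 at 65%.
- With the upper rate kept: 70/0.00290 = about 24,100 visits at 100% capture, or about 37,100 at 65%.

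These are break-even averages. With a Poisson mean of exactly 70, the chance of reaching 70 is only 52%.

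**Cross-check against the 1,420 sepsis patients (section 3.4.2)**

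The end date is not given, so I assume a span of 5 to 6 years. Then 1,420/(5 × 3) = 94.7 and 1,420/(6 × 3) = 78.9 patients per 4 months. To yield 70, a share of 70/94.7 = 74% to 70/78.9 = 89% would have to be eligible, with all of them captured. These are patients treated for sepsis, described without the trial's age, fluid-volume or continuing-poor-perfusion criteria. Section 3.4.1 explains that, because the screen's positive predictive value was 25.4%, "we have required the additional inclusion criterion of administration of at least 20 mL/kg IV/IO fluid resuscitation", together with a judgment that more fluid is likely to be needed. The 1,420 is therefore not an eligible count.

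**The case against.** The strongest objection is that nothing in the design depends on the four-month figure. Recruitment closes at a count, and no endpoint, feasibility criterion or stopping rule uses the accrual window. A slow trial ends later, but it is not biased. This is correct, and it limits the finding to a planning statement.

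A second objection is that the probabilities look firmer than their inputs. The visit count is approximate, and the Poisson model treats both rate and visits as known. This stands in part. With 22,000 visits, an illustrative 10% upward rounding, the upper-rate mean is 63.8 and the chance of 70 or more rises from 6.9% to 23%. The 6.9% should therefore be read as unlikely, not as a precise figure. Rounding still does not close the gap in expectation, which needs about 24,100 visits at the top of the range with no patient missed.

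A third objection is that 65% capture is not a forecast. Section 6.3.2 uses it as a pass mark: "The proportion of eligible patients treated in the pediatric ED who are enrolled, randomized, and treated with study fluid is" required to exceed that level. I agree, and the shortfall does not depend on it, because it is already present at 100%.

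Lastly, the ED's sepsis volume may be larger than the rate implies. The 1,420 figure is compatible with that: a span of 4.5 years would give about 105 per 4 months and a required eligible share of 67%. But its time span is unknown and it is not filtered for eligibility. It suggests that the rate, and not only the duration, may be the faulty input. It does not rescue the sentence as written.

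**Conclusion.** The concern holds. On the figures in section 9.5, four months yields 38 to 58 expected eligible patients against 70 to be randomized, and this assumes that every eligible patient is enrolled. Reaching 70 in that time is unlikely rather than impossible. Using 80 enrolled as the target widens the gap.

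The multiplication rests only on the protocol's own numbers. The probabilities also assume Poisson counts with the stated rate and visits taken as exact. The documents do not show which of the rate, the visit count and the duration is wrong. The consequence is limited to the forecast. The error is definite and worth correcting, but it does not threaten the trial's conclusions.

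**What to change.** Keep 70 randomized. In section 9.5, reconcile the eligible rate, the visit count or the duration, print the multiplication, and state the capture rate assumed. Say whether the forecast is for 70 randomized or for the roughly 80 enrolled in the Synopsis and section 3.3.2.

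- If the rate and visits are right, restate expected accrual to 70 as about 4.8 to 7.4 months at full capture, and lengthen it by the sponsor's own capture assumption. At 65%, as an illustration, it would be 7.4 to 11.4 months.
- If four months is right, give the rate or visit count that supports it, with its capture rate. On average at least 350 per 100,000 is needed, or about 24,100 visits at the upper rate, both at full capture. Note that such averages give only about an even chance of reaching 70 in time.
- If the rate is the faulty input, explain how the eligible rate relates to the 1,420 sepsis patients in section 3.4.2, and give the period over which they were counted.

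The cost is one planning figure that may become less favorable. Sample size, endpoints, analysis and procedures do not change.
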